9.0 SURGERY

A. In the majority of instances, it is recommended that the incision for the lumpectomy and that for the SLNB be separate. A single continuous incision for both the lumpectomy and the axillary sampling is to be avoided and will preclude inclusion on the protocol. This is likely to allow lumpectomy and axillary node sampling cavities to communicate, prohibiting targeting of lumpectomy cavity alone.

B. The cavity must be visible by CT. Placement of 4-6 surgical clips is strongly encouraged. The clips, if placed, are to be attached to the medial, lateral, anterior, posterior, superior and inferior walls of the resection cavity.

NOTE: gold fiducial markers may be used for both cavity delineation and daily kv imaging and image guidance, whereas surgical clips serve to delineate the cavity only. Gold fiducial markers may be placed post-operatively or intraoperatively for use in image guidance. Closure of the resection cavity should be performed to limit seroma fluid accumulation and therefore minimize the target volume.

C. Oncoplastic reconstruction is not allowed.

D. If margins are positive, close (<2mm) or unknown, a re-excision is required prior to study entry.

10.0 OTHER THERAPIES

A. Hormonal therapy is allowed at any time after biopsy or lumpectomy, prior to, during or immediately after radiation, at the discretion of the patient's medical oncologist or other physicians.

B. The use of chemotherapeutic agents prior to or during radiation is not allowed.

C. Chemotherapy regimens should be started no earlier than 2 weeks after the completion of radiation.

11.0 PATHOLOGY

A. Pathology review at Yale of any specimen obtained from referring surgeons from outside institutions will be required for the purposes of this study.

B. Otherwise standard pathologic assessment from Yale will be required.

12.0 PRE AND POST ENROLLMENT PATIENT CALENDAR

A. Study Parameters

Assessment	Pre Rx	During Radiation Therapy	Post RX 4 weeks (+/- 2 weeks)	Post RX 3 mos. (+/- 2 weeks)	Post RX 6 mos. (+/- 2 weeks)	Post RX 1 year (+/- 6 weeks)	Post RX 3 years (+/- 6 weeks)
H&P	X		X	X	X	X ^b	X ^b
Breast exam	X		X	X	X	X ^b	X ^b
Weight	X				X	X ^b	X ^b
Height	X						
Disease status	X					X ^b	X ^b
Toxicity Assessment	X	X	X	X	X	X ^b	X ^b
Bilateral Mammogram	X					X ^c	X ^c
Chest x-ray	X ^a					X ^a	X ^a
CBC, platelets	X						
SGOT, Alk Phos	X						
Serum calcium	X						
Bone scan, Abd. CT.	X ^a						
Patient Reported Cosmesis (BCTOS)	X					X	X
MD Reported Cosmesis	X					X	X
Digital images taken of treated and untreated breasts						X ^d	X ^d
4D CT scan for planning	X						
Urine Pregnancy Test (ages 10-60, and of childbearing potential)	X						
Breast Pain Questionnaire						X ^{d,e}	X ^d

X to be performed routinely

X^a if clinical symptoms or lab values warrant

X^b as per standard practice

X^c Bilateral mammograms will occur at least annually (+/- 6 weeks following the preceding bilateral mammogram), or as clinically indicated.

X^d If patient consents

X^e Patients who have passed the 1-year assessment point will be asked to complete the questionnaire as soon as possible.

As is standard for evaluation of radiation toxicity, patients will be followed for three years. For the first 90 days post-treatment, the RTOG acute toxicity scale will be used, and for up to three years the RTOG/EORTC late toxicity scale will be used. Any additional toxicities that do not meet the criteria for RTOG scoring will be recorded according to the Common Terminology Criteria for Adverse Events (CTCAE) version 4.0 guidelines.

B. Patient Enrollment Sheet

C. Complete History and Physical Examination

D. Mammographic Report(s)

E. Pathology Reports

F. Initial Radiation Therapy Consult Note

G. Patient Treatment Data

H. Toxicity Reports

Skin reaction(s) to radiation, including erythema, desquamation, etc. and any radiation complications or unusual or severe side effects of treatment will be recorded using RTOG acute and RTOG/ECOG late toxicity scoring. All toxicity from radiation is described in both acute and late terms, and this is often grouped together, because radiation delivery can lead to either side effect for normal tissue. Specifically, RTOG acute and RTOG/ECOG late radiation toxicity scoring parameters were originally described for breast conservation treatment, and will be used in this study.³³ Acute toxicity includes any side-effects during treatment or within three months following treatment and late toxicity includes side-effects from three months up to three years in this study (see Appendix III and IV). Both acute and late toxicity use scores from 0-5. Toxicity is not expected for other tissues but will be documented. Excess toxicity will be reported as detailed below (Section 14 and Section 15).

I. Copies of Dosimetry Calculations (see Appendix VI).

J. Patient Follow Up

Patient follow up will occur 4 weeks, 3 months, 6 months, 1 year, and three years post Radiation Therapy. Some patients will be followed beginning 4 weeks after treatment at L&M because it is closer to home for them. In these cases, [name] will be meeting with the patients.

- Vital status. If patient has expired, a data form must be submitted.
- Disease status, classified local, elsewhere, contralateral, regional, or distant. A local failure is defined as an ipsilateral breast tumor recurrence within the same quadrant of the breast as the original lumpectomy. An elsewhere failure is defined as an ipsilateral breast tumor recurrence not inside the same quadrant as the original lumpectomy. A contralateral breast cancer is defined as a breast cancer in the opposite breast. A regional failure is a recurrence in the axilla, internal mammary nodal chain, or supraclavicular lymph node basins. A distant failure is any metastasis to distant organs (i.e. bone, lung, liver, brain).
- Toxicity evaluation.
- Follow-up physical examination and mammographic results.

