8.0 ASSESSMENT OF TOXICITY, COSMESIS, BREAST PAIN, AND SATISFACTION

The purpose of this study is to evaluate the feasibility of using image guidance and four-dimensional computed tomography to reduce the volumes of non target breast tissue that is treated with accelerated partial breast irradiation via the external beam technique. However, toxicity will be assessed and a larger trial will be planned to formally assess the presence or absence of improved cosmesis with this technique. Some patients who were originally referred to Yale-New Haven Smilow from Lawrence & Memorial (L&M) Hospital for this trial will be followed beginning 1 month after treatment at L&M because it is closer to home for them. [name] also works at Lawrence & Memorial. In these cases, [name] will be meeting with the patients for standard radiation therapy follow up and assessment of cosmesis. No treatment procedures will occur there.

A. The Breast Cancer Treatment Outcome Scale (BCTOS) will be used to assess cosmetic results using patient self-report. This brief self-report instrument has high reliability and validity, and has been used in a variety of previous studies on recovery from breast cancer treatment. The first patient-rated cosmetic evaluation will occur after informed consent but prior to completion of treatment (baseline). The BCTOS will be used to assess cosmesis at baseline, 1-year, and 3 year follow-up.

B. Treating radiation oncologist cosmesis assessment will occur at baseline, and 1 year, and 3 years post Radiation Therapy, and will be graded according to the Harvard Cosmesis Scale (Appendix V). Toxicity assessment will occur at 1 month, 3 months, 6 months, 1 year, and 3 years post Radiation Therapy, and will be graded according to RTOG.

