14.0 EXPECTED SIDE-EFFECTS AND ADVERSE EVENTS

A. Expected side effects

The side effects expected in this trial are not predicted to be significant, and should be similar to those experienced in the previously reported trials. Expected toxicities and relative incidences over time are given from Berrang et al. It is important to note that in addition to this list, Hepel et al reported 5/60 grade 3 toxicities, 4 of which were subcutaneous fibrosis, and one which was rib fracture and pericarditis. This group also reported one grade 4 subcutaneous toxicity, which was a patient who required wide local excision for severe breast pain at the site of APBI, and later underwent mastectomy for non-healing ulceration at the same site. This is the only toxicity higher than grade 3 reported in the literature (1 of a combined 3D CRT PBI PUBLISHED experience of 348, or 0.2%). If unexpected severe toxicities arise then we will follow early stopping and reporting guidelines as detailed in Section 15.

Table 3. Treatment-related toxicities

Toxicity	Before RT (n = 104)			1 year after RT (n = 91-88)			3 years after RT (n = 87-85)		
	Grade 0	Grade 1	Grade 2+	Grade 0	Grade 1	Grade 2+	Grade 0	Grade 1	Grade 2+
Breast pain	88%	11%	1%	74%	23%	3%	77%	23%	0%
Edema	68%	31%	1%	84%	11%	5%	94%	6%	0%
Dermatitis	90%	8%	2%	99%	1%	0%	100%	0%	0%
Fatigue	84%	13%	3%	96%	4%	0%	91%	8%	1%
Hyperpigmentation	90%	7%	3%	70%	26%	4%	88%	11%	1%
Hypopigmentation	97%	3%	0%	90%	10%	0%	94%	5%	1%
Induration	54%	40%	6%	64%	33%	3%	61%	31%	8%
Telangiectasia	91%	9%	0%	93%	5%	2%	80%	13%	7%

B. Assessing Adverse Events

All toxicities possibly, probably or definitely related to Radiation Therapy will be scored using RTOG acute and RTOG/EORTC late toxicity guidelines (see Appendix III and IV). Adverse events will be described and reported as described in Section 15.

Any additional toxicities will be recorded according to the Common Terminology Criteria for Adverse Events (CTCAE) version 4.0 guidelines.

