GENITOURINARY	No change	Frequency of urination or nocturia twice pretreatment habit/dysuria, urgency not requiring medication	Frequency of urination or nocturia which is less frequent than every hour. Dysuria, urgency, bladder spasm requiring local anesthetic (e.g. Pyridium)	Frequency with urgency and nocturia hourly or more frequently/dysuria, pelvis pain or bladder spasm requiring regular, frequent narcotic. Gross hematuria with/without clot passage	Hematuria requiring transfusion/acute bladder obstruction not secondary to clot passage, ulceration or necrosis
HEART	No change over baseline	Asymptomatic but objective evidence of EKG changes or pericardial abnormalities without evidence of other heart diseases	Symptomatic with EKG changes and radiologic findings of congestive heart failure or pericardial disease/no specific treatment required	Congestive heart failure, angina pectoris, pericardial disease responding to therapy	Congestive heart failure, angina pectoris, pericardial disease, arrhythmias not responsive to non-surgical measures

CNS	No change	Fully functional status (i.e., able to work) with minor neurologic findings, no medication needed	Neurologic findings present sufficient to require home care/nursing assistance may be required/medications including steroids/anti-seizure agents may be required	Neurologic findings requiring hospitalization for initial management	Serious neurologic impairment which includes paralysis, coma or seizures > 3 per week despite medication/hospitalization required
HEMATOLOGY	WBC (X 1000)	=> 4.0	3.0 -<4.0	2.0-<3.0	1.0-<2.0
PLATELETS (X 1000)		>100	75-<100	50-<75	25-<50
NEUTROPHILS (X 1000)		=>1.9	1.5-<1.9	1.0-<1.5	0.5-<1.0
HEMOGLOBIN (X 1000)		>11	11-9.5	<9.5-7.5	<7.5-5.0
HEMATOCRIT (%)		=>32	28-32	<28	Packed cell transfusion required
GUIDELINES: The acute morbidity criteria are used to score/grade toxicity from radiation therapy. The criteria are relevant from day 1, the commencement of therapy, through day 90. Thereafter, the EORTC/RTOG Criteria of Late Effects are to be utilized. The evaluator must attempt to discriminate between disease and treatment related signs and symptoms An accurate baseline evaluation prior to commencement of therapy is necessary. All toxicities Grade 3,4, or 5* must be verified by [name] * ANY TOXICITY WHICH CAUSED DEATH IS GRADED 5.					

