APPENDIX IV

RTOG / EORTC Late Radiation Morbidity Scoring Scheme						
	0	1	2	3	4	5
SKIN	NONE	Slight atrophy; Pigmentation change; Some hair loss	Patch atrophy; Moderate telangiectasia; Total hair loss	Marked atrophy; Gross telangiectasia	Ulceration	
SUBCUTANEOUS TISSUE	NONE	Slight induration (fibrosis) and loss of subcutaneous fat	Moderate fibrosis but asymptomatic; Slight field contracture; <10% linear reduction	Severe induration and loss of subcutaneous tissue; Field contracture >10% linear measurement	Necrosis	D E A T H
MUCOUS MEMBRANE	NONE	Slight atrophy and dryness	Moderate atrophy and telangiectasia; Little mucous	Marked atrophy with complete dryness Severe telangiectasia	Ulceration	R E C T L Y
SALIVARY GLANDS	NONE	Slight dryness of mouth; Good response on stimulation	Moderate dryness of mouth; Poor response on stimulation	Complete dryness of mouth No response on stimulation	Fibrosis	R E L A T E D
SPINAL CORD	NONE	Mild L'Hermitte's syndrome	Severe L'Hermitte's syndrome	Objective neurological findings at or below cord level treated	Mono, para quadriplegia	T O R A D
BRAIN	NONE	Mild headache; Slight lethargy	Moderate headache Great lethargy	Severe headaches; Severe CNS dysfunction (partial loss of power or dyskinesia)	Seizures or paralysis Coma	

SYSTEM	GRADE	SYMPTOMS			ADDITIONAL INFORMATION
		GRADE 1	GRADE 2	GRADE 3	
EYE	NONE	Asymptomatic cataract Minor corneal ulceration or keratitis	Symptomatic cataract Moderate corneal Ulceration; Minor retinopathy or glaucoma	Severe keratitis; Severe retinopathy or detachment Severe glaucoma	Panophthalmitis/Blin dness
LARYNX	NONE	Hoarseness; Slight Arytenoid edema	Moderate arytenoid edema; Chondritis	Severe edema; Severe chondritis	Necrosis
LUNG	NONE	Asymptomatic or mild symptoms (dry cough) Slight radiographic appearances	Moderate symptomatic fibrosis or pneumonitis (severe cough) Low grade fever; Patchy radiographic appearances	Severe symptomatic fibrosis or pneumonitis Dense radiographic changes	Severe respiratory insufficiency/ Continuous o2/Assisted ventilation
HEART	NONE	Asymptomatic or mild symptoms; Transient T wave inversion & ST changes; Sinus tachycardia>110 (at rest)	Moderate angina on effort Mild pericarditis; Normal heart size; Persistent abnormal T wave and ST changes; Low ORS	Severe angina; Pericardial effusion; Constrictive pericarditis; Moderate heart failure; Cardiac enlargement; EKG abnormalities	Tamponade/Severe heart failure/Severe constrictive pericarditis

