Appendix VI

Patient reported Breast Cancer Treatment Outcome Scale (Stanton AL, Krishnan L, Collins CA. Form or function? Part 1. Subjective cosmetic and functional correlates of quality of life in women treated with breast-conserving surgical procedures and radiotherapy. *Cancer*. 2001;91:2273–2281.)

We are interested in your evaluation of your physical appearance and functioning since your breast surgery and/or radiation.

Please rate the following items on this four-point scale, according to your evaluation at this time: 1) no difference between treated and untreated breast and area, 2) slight difference between treated and untreated breast and area, 3) moderate difference between treated and untreated breast and area, and 4) large difference between treated and untreated breast and area.

After rating all items, you are asked to place a check by any difference that was bothersome.

	1	2	3	4
Breast Size	No difference	Slight difference	Moderate difference	Large Difference
Breast texture/hardening	No difference	Slight difference	Moderate difference	Large Difference
Nipple appearance	No difference	Slight difference	Moderate difference	Large Difference
Breast Pain	No difference	Slight difference	Moderate difference	Large Difference
Breast Tenderness	No difference	Slight difference	Moderate difference	Large Difference
Breast Shape	No difference	Slight difference	Moderate difference	Large Difference
Breast Elevation (how high the breast is)	No difference	Slight difference	Moderate difference	Large Difference
Scar Tissue	No difference	Slight difference	Moderate difference	Large Difference
Fit of Bra	No difference	Slight difference	Moderate difference	Large Difference
Breast Sensitivity	No difference	Slight difference	Moderate difference	Large Difference
Fit of Clothing	No difference	Slight difference	Moderate difference	Large Difference

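### Secondary endpoint, cheap improvement: no fibrosis grade is required before radiation, so the late fibrosis rate and its dose correlations would mix surgical with radiation induration

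*Combined protocol and SAP*

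**What the plan says.** - **Endpoint.** Section 3.0 B makes subcutaneous fibrosis over the first three years an endpoint. Sections 2.0 B and 3.0 C plan to relate dose parameters to toxicity, and 3.0 C names subcutaneous toxicity. Neither section 3.0 nor section 13.0 says whether fibrosis is an absolute grade or a change.
- **Scale.** Fibrosis of the breast is graded in the subcutaneous row of Appendix IV, where grade 1 is "Slight induration (fibrosis) and loss of subcutaneous fat" and grade 0 means none at all. The acute table in Appendix III has no such row.
- **When the scale applies.** Section 12.0 A uses the acute scale for the first 90 days; after that, "for up to three years the RTOG/EORTC late toxicity scale will be used". Section 12.0 H agrees: "late toxicity includes side-effects from three months up to three years in this study".
- **Baseline.** The calendar marks a toxicity assessment and a breast exam before treatment, and the Appendix III guidelines say "An accurate baseline evaluation prior to commencement of therapy is necessary". Neither names an instrument or a grade. Section 8.0 B lists only later visits: "Toxicity assessment will occur at 1 month, 3 months, 6 months, 1 year, and 3 years post Radiation Therapy".
- **Other baseline information.** Physician-rated Harvard cosmesis is recorded at baseline. So is the patient-reported BCTOS, which includes the item "Breast texture/hardening"; section 8.0 A lets its baseline be taken at any time until treatment is completed.

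**The concern.** Every patient has had a lumpectomy, and surgery itself can leave induration. Grade 0 in the Appendix IV row is absolute, unlike acute skin grade 0, which is defined relative to baseline. A late grade on that row therefore carries no correction for what was there before radiation. The protocol already accepts the principle for cosmesis: the expectation in 2.0 B is conditioned on patients who start at a good or excellent baseline.

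Two secondary results are affected.

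- **The fibrosis rate.** Without a graded baseline, the rate cannot be read as a radiation effect.
- **The dose correlations.** Section 9.0 B says large seromas can make it hard to limit dose outside the target. If large seromas also leave more surgical induration (an assumption; the protocol does not say so), dose and induration would be associated even with no dose effect.

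Section 13.0 B places toxicity beside the question of whether the technique deserves a larger trial, so these results will be read.

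**Working it through.** The documents state no sample size, alpha or power for fibrosis, so there is no planned figure to reproduce.

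**1. Timing.** Taking 3 months as 91 days, the 3-month visit (± 2 weeks) falls on days 77 to 105 and straddles day 90. For some patients the first late-scale fibrosis grade may not come until 6 months.

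**2. Reference rates.** Section 14.0 A introduces its table as "Expected toxicities and relative incidences over time". Its induration row reads:

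| | Grade 0 | Grade 1 | Grade 2+ | Any |
|---|---|---|---|---|
| Before radiation | 54% | 40% | 6% | 46% |
| 1 year | 64% | 33% | 3% | 36% |
| 3 years | 61% | 31% | 8% | 39% |

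At 46%, about 28 of 60 patients (section 3.0 D) or 32 of 70 (section 13.0 C) would have induration before any radiation.

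**3. What the margins alone allow.** With baseline prevalence B and follow-up prevalence F, the new-onset proportion lies between max(0, F − B) and min(F, 1 − B).

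- New grade 1+ at 3 years: max(0, 0.39 − 0.46) = 0 to min(0.39, 0.54) = 39%.
- New grade 2+ at 3 years: 0.08 − 0.06 = 2% to 8%, or 1.2 to 4.8 of 60 (1.4 to 5.6 of 70).
- New-or-worsened at 3 years, by linear programme over all 3 × 3 joint tables: 2% to 39%, or 1.2 to 23.4 of 60 (1.4 to 27.3 of 70).
- New-or-worsened at 1 year, same method: 0% to 36%, or 0 to 21.6 of 60.

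As a point of reference inside the bounds, if baseline and 3-year status were independent, new grade 1+ would be 0.54 × 0.39 = 21% (13 of 60).

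Attrition barely matters. The table has 104 patients before radiation and 85 to 87 at 3 years. If all 17 to 19 patients lost had baseline induration, the remaining baseline rate would be (47.8 − 17)/87 = 35.4% to (47.8 − 19)/85 = 33.9%. The lower bound for new grade 1+ would rise only to about 4% to 5%.

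**4. Confounding of a dose comparison.** All of the following is assumed: n = 60 split at the median dose (30 per half), no dose effect, two-sided 5% test. Let s be the share of all patients with persistent surgical induration. Persistence among those indurated at baseline is s/0.46, and new onset among the rest is m = (0.39 − s)/(1 − s). A half with baseline prevalence b has a 3-year rate of b·s/0.46 + (1 − b·s/0.46)·m.

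| Baseline, low vs high dose | s | 3-year rate, low vs high | Unadjusted error | Stratified by baseline |
|---|---|---|---|---|
| 34.5% vs 57.5% | 0.1 | 37% vs 41% | 6% | 5% |
| | 0.2 | 35% vs 43% | 9% | 5% |
| | 0.3 | 32% vs 46% | 18% | 5% |
| 23% vs 69% | 0.1 | 36% vs 42% | 8% | 5% |
| | 0.2 | 31% vs 47% | 22% | 5% |
| | 0.3 | 26% vs 52% | 55% | 5% |

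The stratified test is Mantel-Haenszel, by simulation.

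**5. Power.** With equal baselines and an assumed risk ratio of 3, power at s = 0.1/0.2/0.3 is 64%/32%/11% unadjusted, about 65%/35%/13% stratified, and 53%/38%/16% if restricted to baseline-free patients (16 per half). Stratifying protects against confounding; it does not buy material power.

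**The case against.** **Nothing planned is broken.** A reader might infer that a planned change-from-baseline analysis cannot be computed. The documents do not support that. Section 3.0 B words fibrosis as something to measure, no change analysis is defined, and nothing forbids an investigator from scoring the row before treatment. The success rule is purely dosimetric, and section 8.0 leaves the formal test of cosmesis to a larger trial. This stands.

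**The 14.0 A table may not be on the Appendix IV scale.** Its scale is not stated, and it grades fatigue and breast pain, which have no row in Appendix III or IV. This stands: every figure above carries that assumption.

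**The wide bounds overstate the problem.** A reader might take 2% to 39% as a plausible range. It spans every possible joint table and is driven by grade 1; for grade 2+ it is 2% to 8%. Nothing here shows distortion of a grade 3 or higher rate. This stands.

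**The 55% is built from assumptions.** It needs a 23% vs 69% imbalance and 30 of the 39 percentage points at 3 years to be surgical. The protocol names no test, alpha or dose split. Its 30% cap on the cavity-to-breast ratio and its exclusion of changing seromas narrow the assumed pathway. This stands as to size; the direction of the risk remains.

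**Existing provisions help.** Section 15.0 B records all adverse events with attribution, and Appendix III asks evaluators to separate disease-related from treatment-related signs. This helps only in part. Section 14.0 B still scores findings that are only possibly related, and attribution without a graded baseline rests on recall or ungraded notes. Harvard cosmesis is not a fibrosis grade, and the BCTOS items are patient-reported. CTCAE is a fallback for events that RTOG/EORTC does not describe, and subcutaneous fibrosis is described there.

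**Conclusion.** The point holds as a low-cost improvement to a secondary endpoint. As written, the plan does not require the one subcutaneous fibrosis grade in its appendices to be scored before radiation. Its late fibrosis rate will therefore include surgical induration in an unknown proportion, and its fibrosis dose correlations are open to confounding by that induration.

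The size is uncertain. If the 14.0 A rates carried over to Appendix IV, nearly half of patients would have induration at baseline, and late grades alone would not show how much of the 39% at 3 years is new. Confounding is possible but unmeasured: it is slight under the milder assumed imbalance with little persistence and serious only under the extreme one.

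**What to change.** - **Assessment (8.0 B and 12.0).** Score the Appendix IV subcutaneous row at the existing pre-treatment breast exam and at every later visit, including those before day 90. Record attribution in a separate field.
- **Reporting (3.0 B).** Give both the absolute grade and the new-or-worsened grade relative to pre-treatment.
- **Dose correlations (2.0 B, 3.0 C).** For fibrosis, adjust for or stratify by baseline grade. Do not restrict to baseline-free patients.
- **Patients already treated.** Abstract the baseline from the pre-treatment exam note where it permits, flag it as retrospective, and show results with and without these patients.

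**Cost.** One graded row at visits already scheduled. Retrospective baselines are less reliable. This is version 9 and some patients have passed one year; the documents do not say how many could still have a prospective baseline. A change score can also miss surgical induration that resolved and was replaced by new fibrosis of the same grade, which is why the absolute grade must be reported too.
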